Rationale	This protocol is designed to identify participants who have persistent peanut allergy. By specifically targeting participants who are at the highest risk for life-long peanut sensitivity, we anticipate that we might maximize the benefits of desensitization and/or clinical tolerance induction. By including in our protocol design a post-therapy challenge after a significant allergen avoidance period, we will better distinguish true tolerance from desensitization and some of the immune changes associated with varying clinical outcomes. A blinded placebo control group is included, to control for possible changes in clinical sensitivity over time independent of therapy. The selection of older adolescents and adults will also allow us to better	
Clinical Phase	1/11	
Mechanistic Study	✓ Yes No	
IND Sponsor	[name], PhD	
Principal Investigator	[name], PhD	
Participating Site(s)	Massachusetts General Hospital	
Accrual Objective	40	
Study Objective	To determine whether PN OIT induced clinical tolerance in the context of food allergy is significantly associated with the expansion of a specific regulatory T cell subset (CD45RA- CD25++ FoxP3++) that is thought to be inducible in the gut-associated lymphoid compartment and associated with immunological tolerance.	
Study Design	Single-center, double blind, placebo controlled, randomized trial of peanut OIT in adolescents and adults (7 to 55 years)	
Study Duration	Approximately 74 weeks	
Primary Endpoint	The difference in the proportion of induced Treg cells (CD45RA- CD25++ FoxP3++ of CD4+ T cells) from baseline to the end of maintenance therapy.	

SYNOPSIS CONTINUED

Tolerance:

• The change in median eliciting dose (ED) from DBPCFC1 to DBPCFC3.

Desensitization:

- The change in median eliciting dose (ED) from DBPCFC1 to DBPCFC2.
- The frequency of accidental ingestion reactions in active versus control treatment.

Secondary Endpoints (Clinical)

Safety:

- Anaphylaxis requiring more than 1 administration of epinephrine; or hospitalization.
- Death as a result of the investigational product.
- The rate of reported adverse advents due to accidental ingestions in the active versus placebo groups.

SYNOPSIS CONTINUED

The change in the TCR clonal diversity of in vitro allergen-expanded Treg cells and induced Treg cells measured by $TCR\beta$ CDR3 sequence clonotyping of sorted cells during active treatment among participants who achieve increased clinical tolerance (Tolerance and Partial Tolerance Groups as defined in clinical endpoints) versus the Treatment Failure Group. The change in ED of end-point dilution skin testing between actively treated and placebo treated participants following maintenance therapy. • The change in ED of end-point dilution skin testing among actively treated participants following maintenance therapy and avoidance between clinical outcome groups. Secondary Endpoints (Mechanistic) • The change in peanut-specific basophil ED in actively treated participants at the end of maintenance and the end of avoidance between clinical outcome groups. • The change in peanut allergen-specific IgG4 in actively treated participants by the end of maintenance between clinical outcome groups. • The change in Ara h 2 specific surface and secreting B cells between baseline (measured at 12 weeks of treatment) and the end of maintenance. • Statistically significant gene expression changes by transcriptional profiling of regulatory and effector T cell participants before and after OIT between clinical outcome groups. Diagnosis of peanut allergy by medical history • Evidence of peanut-specific IgE by either: positive skin prick test to peanut (reaction wheal at least 5 mm larger than saline control) or serum peanut-specific IgE \geq 5 kU/L at screening visit. Ara h 2 specific IgE >0.35 kU/L at screening visit. Inclusion Criteria • Who are willing to sign informed consent or whose parent or legal guardian is willing to sign the consent form (age appropriate) • Who are willing to sign the assent form, if age appropriate Males and females of all ethnic/racial groups aged 7-55 years old who are otherwise healthy. React to ≤443 mg of peanut protein during DBPCFC1

SYNOPSIS CONTINUED

STROP SIS CONTINUED	
Exclusion Criteria	 History of severe anaphylaxis Severe or Moderate asthma Poorly controlled asthma Diagnosis of other severe or complicating medical problems, including autoimmune or chronic immune inflammatory conditions or gastrointestinal inflammatory conditions Inability to cooperate with and/or perform oral food challenge procedures Primary Immune Deficiency Allergy to oat confirmed by skin prick testing and history Current use of beta blockers, angiotensin converting enzyme inhibitors, or monoamine oxidase inhibitors Women of childbearing potential who are pregnant, planning to become pregnant, or breastfeeding Use within the past 6 months of other systemic immunomodulatory treatments Hematocrit <0.36 for adult females or <0.38 for adult males Weight <23 kg
Investigational Product / Intervention	Active peanut flour vs. placebo oat flour
Study Procedures	OIT, DBPCFCs, physical examination, pregnancy testing, phlebotomy, PFTs
Statistical Considerations	n=40, 3:1 active to placebo; Per protocol analysis of the Treg proportion by clinical outcome for the anticipated 22 subjects completing DBPCFC3; effect size of 1.5 for primary outcome [?]; 27% (n=8) combined Partial Tolerance / Tolerance versus Treatment Failure (n=14).

Contents

1	BAC	CKGROUND AND RATIONALE	12
	1.1	Background	12
	1.2	Rationale for Selection of Study Population	12
	1.3	Investigational Product(s) / Intervention(s)	12
	1.4	Rationale for Selection of Investigational Product(s) / Intervention(s) and Regimen	13
	1.5	Preclinical and Clinical Experience	13
		1.5.1 Preclinical Studies	13
		1.5.2 Clinical Studies	14
	1.6	Risks	14
		1.6.1 Risks of Investigational Product(s) / Intervention(s)	14
		1.6.2 Risk of Study Procedures	14
		1.6.2.1 Double-blind placebo controlled food challenge (DBPCFC)	14
		1.6.2.2 Desensitization Procedure	15
		1.6.2.3 Allergy Prick Skin Testing	15
		1.6.2.4 Blood Draw	15
		1.6.3 Risk of Concomitant Medications, Prophylactic Medications and Rescue Medications	15
	1.7	Benefits	16
	• • •	1.7.1 Benefits of Investigational Product(s) / Intervention(s)	16
		1.7.2 Benefits of Study Procedure(s)	16
		1.7.2 Deficites of Study Frocedure(s)	10
2	OBJ	IECTIVES	16
	2.1	Primary Objective(s)	16
	2.2	Secondary Objective(s)	16
		2.2.1 Clinical:	16
		2.2.2 Mechanistic:	17
		2.2.3 Exploratory:	17
			• •
3	STU	DY DESIGN	17
	3.1	Study Endpoints	18
		3.1.1 Primary Endpoint(s)	18
		3.1.2 Secondary Endpoint(s)	18
	3.2	Study Completion	19
4	SEL	ECTION AND WITHDRAWAL OF PARTICIPANTS	19

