- **1.6.2.4 Blood Draw** May aggravate a pre-existing anemic condition but this risk is negligible since the volume of blood to be drawn at each visit will be at most 3 ml/kg in pediatric participants and 1 unit of blood in adult participants. Blood draws will occur four times spread out over the 90 week study (See Section 7 for specific schedule). Other risks are those related to any needle puncture, including slight bruising, local infection, or the possibility of the participant fainting. The discomfort involved is minimal.

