7.4.4 Maintenance Visits (Days 350-434)

Maintenance visits will occur on the MGH CRC monthly during the 12 weeks of maintenance therapy. Each visit will involve a medical history and physical examination. The medical history will consist of a structured interval clinical history and review of systems concerning any types of allergic symptoms related to their food allergy, atopic dermatitis or asthma. The participants and/or their parents will record any known accidental ingestion that occurs during the study. The physical exam will include vital signs, and spirometry. A negative urine pregnancy test will be documented for female participants of child-bearing potential; if the test is positive, the visit will be cancelled and if pregnancy is confirmed, the subject will be withdrawn from the study.

Blood will be collected and skin prick testing will be performed at three follow-up visits for research laboratory studies at baseline, on maintenance therapy (after 12 weeks at 4000 mg of peanut protein or maximum tolerated) prior to DBPCFC2, and prior to DBPCFC3 (12 weeks post avoidance). An additional blood draw will occur during build up (12 weeks after beginning treatment). Blood will be drawn by trained study staff or Clinical Research nurses. Urine will be collected from female participants for a Human Chorionic Gonadotropin (HCG)-based pregnancy test at all follow up visits throughout the study.

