7.4.5 Double-Blind Placebo-Controlled Food Challenge 2 (Day 434)

After taking maintenance dose for 12 weeks, participants will come to MGH CRC for their second double-blind, placebo-controlled food challenge (DBPCFC2).

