7.4.7 Double-Blind Placebo-Controlled Food Challenge 3 (Day 518)

After 12 weeks of complete peanut avoidance after the DBPCFC2, participants will come to MGH CRC for their third double-blind, placebo-controlled food challenge (DBPCFC3). The DBPCFC3 will be similar to DBPCFC2, differing only in the dosing schedule. See Section 7.7.1 for details.

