7.7.6 Phlebotomy

At visits 0, 27 and 30, 3ml/kg (for participants <18 years and/or participants weighing <50 kg) or 1 unit (550 ml) of blood will be obtained by standard venipuncture at the MGH blood bank. One (1) ml of blood will be used to measure peanut specific IgE, IgG, and IgG4. Five (5) ml of blood will be used to measure basophil activation. The remaining blood will be used for mechanistic T cell and B cell studies. Prior to each scheduled large blood draw, a rapid test of hemoglobin level will be performed.

The following criteria will be used to determine for adult participants whether the proposed 550 ml can be drawn:

- AGE must be at least 18 years old
- WEIGHT must be greater than 110 lbs (50 kg);
- PULSE must be between 50 and 100 beats/minute with no cardiac irregularity;
- TEMPERATURE must not exceed 37.55°C or 99.5°F;
- Hematocrit < 0.36 for adult females or < 0.38 for adult males;

An additional blood collection of \leq 200 ml (adults) and 3ml/kg (children) will occur after 12 weeks of treatment to be used for mechanistic B cell studies. For B cell studies, 100-200 million PBMCs will be used for affinity single-cell sorting of Arah2-specific B cells by flowcytometry (see Patil et al. 2015 JACI) as well as bulk sorting of CD19+ CD27+ IgM- cells. These will be used for cloning of functional mAbs and next generation sequencing of BCR, respectively.

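### The schedule of events dates the on-maintenance IgG4 sample to Day 448, two weeks after maintenance ends, in conflict with the endpoint and with sections 7.4.4 and 7.7.6

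*Combined protocol and SAP*

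**What the plan says.** The Synopsis and section 3.1.2 define the endpoint as "The change in peanut allergen-specific IgG4 in actively treated participants by the end of maintenance between clinical outcome groups". Four other places bear on when the sample is taken:

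- **Section 7.4.4** has the research blood drawn "on maintenance therapy (after 12 weeks at 4000 mg of peanut protein or maximum tolerated) prior to DBPCFC2". It speaks of research laboratory studies in general and does not name IgG4.
- **Section 7.7.6** sets the large draws at visits 0, 27 and 30 and does name the assay: "One (1) ml of blood will be used to measure peanut specific IgE, IgG, and IgG4".
- **Section 16.1, sIgE/IgG4 row**, marks screening, then Day 448 in the Maintenance column, then the Avoidance column. The Maintenance column is headed Days 350-434.
- **Section 16.1, T-cell, basophil and titration skin-test rows**, mark Visit 27 in that same Maintenance column.

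Section 16.1 marks OIT dosing through the Maintenance column and not beyond. Section 7.4.7 places DBPCFC3 "After 12 weeks of complete peanut avoidance after the DBPCFC2".

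**The concern.** The endpoint compares an on-treatment IgG4 change between clinical outcome groups. A sample on Day 448 would come after a challenge of up to 4443 mg of peanut protein and, on nominal days, two weeks into avoidance. It would also not be concurrent with the Treg, basophil and skin-test values beside which it is naturally read.

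There is a second risk at this single centre. If staff work from the schedule for some participants and from the text for others, on-dose and off-dose samples would be mixed in one comparison. That comparison is small: the Synopsis expects 8 tolerant or partially tolerant participants against 14 treatment failures among those completing DBPCFC3.

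**Working it through.** The check is day arithmetic followed by a comparison of the sections.

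**Inputs.** Maintenance starts on Day 350 and lasts 12 weeks (7.4.4, 7.4.5). DBPCFC2 is on Day 434 (7.4.5) and DBPCFC3 on Day 518 (7.4.7). Visits 26 to 28 fall in maintenance, and visit 28 is DBPCFC2 (16.1). Maintenance visits are monthly (7.4.4). The general visit window is ±14 days (7.6).

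**The plan's own days reproduce.**
- End of maintenance: 350 + 12 × 7 = 434, as stated.
- End of avoidance: 434 + 12 × 7 = 518, as stated.

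**Position of Day 448.**
- 448 − 434 = 14 days after the end of maintenance and DBPCFC2.
- 518 − 448 = 70 days, or 10 weeks, before DBPCFC3.
- Day 448 therefore lies outside its own column (350-434) and in nominal avoidance.

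**Position of Visit 27.** The documents give no day for it. Assume monthly means every 28 days from Day 350:
- Visits 26, 27 and 28 fall on Days 350 + 28 = 378, 350 + 56 = 406 and 350 + 84 = 434.
- With the ±14-day window, Visit 27 can fall on Days 392 to 420, still before Day 434.
- Gap between the Visit 27 assays and a Day 448 sample: 448 − 406 = 42 days.
- Visit 27 is (406 − 350) / 7 = 8 weeks into maintenance and 434 − 406 = 28 days before its end.

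**The sources side by side.**

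| Source | Timing of the sample | On dosing? | Before DBPCFC2? |
|---|---|---|---|
| Endpoint (Synopsis, 3.1.2) | By the end of maintenance, Day 434 | Yes | Not stated |
| 7.4.4 | After 12 weeks of maintenance, about Day 434 | Yes | Yes |
| 7.7.6 | Visit 27, about Day 406 | Yes | Yes |
| 16.1, sIgE/IgG4 row | Day 448 | No, on nominal days | No, on nominal days |

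Only the schedule cell places the sample after dosing. The two text sections agree that it comes first, but they differ from each other by about four weeks.

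**The case against.** The strongest reply is that one cell is out of line with everything else. It stands under a Maintenance heading that it contradicts, and both text sections put the sample on dosing. That stands, and it limits the finding. A reader might infer that the trial will not measure its stated IgG4 endpoint, but this would treat the outlying cell as governing, and nothing in the documents gives it that priority.

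Day 448 may also have an innocent origin. It equals Day 434 plus the 14-day window. It is also the last day of a two-week challenge period starting on Day 434, if the period that 7.4.1 gives for DBPCFC1 applies to DBPCFC2. The documents state neither explanation. The second would not remove the problem, because the sample could still follow the peanut challenge day.

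Three further inferences are tempting but unsupported:

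- **Selective loss among treatment failures.** A reader might infer that participants who fail DBPCFC2 and return to avoidance would miss a Day 448 sample. But the failure definition also covers those who never reach the minimum maintenance dose, who would lack an end-of-maintenance sample on any draw day. The documents do not say how many participants would fail at DBPCFC2 itself. If the population of section 9.2.2 (active participants completing DBPCFC3) is used for IgG4, this loss does not arise.
- **No room for another draw.** Section 1.6.2.4 says "Blood draws will occur four times spread out over the 90 week study". That count appears already to leave out the 10 ml screening draw in 7.2, so it cannot exclude another small draw.
- **No visit on Day 448.** Section 16.1 lists visits 29 to 31 between Days 434 and 518. Section 7.4.6 dates only one visit before DBPCFC3, four weeks ahead of it, so an undated visit near Day 448 cannot be ruled out.

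**Conclusion.** The point holds as an internal inconsistency that changes what a named secondary endpoint would measure if the schedule were followed. Day 448 is 14 days after the end of maintenance and DBPCFC2; this follows from the plan's own nominal days and needs no assumption. The 42-day gap from the other on-maintenance assays, and the placing of Visit 27 at about week 8, rest on 28-day spacing of the maintenance visits.

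The documents do not show that the sample will in fact be taken late, nor how far a two-week delay would move IgG4, so no bias can be quantified. The T-cell sample for the primary Treg endpoint is marked Visit 27, so the Day 448 entry does not touch it. The correction is worth making because the schedule is a working document for staff and the comparison is small.

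**What to change.** In 16.1, replace Day 448 in the sIgE/IgG4 row with the pre-DBPCFC2 on-maintenance draw used for the T-cell and basophil assays. Section 7.7.6 already allocates 1 ml for the serology, so no blood draw is added.

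That change alone does not put the sample at the end of maintenance. Visit 27 (about Day 406) and the 12 weeks in 7.4.4 (about Day 434) must be reconciled in 7.4.4, 7.7.6 and 16.1, so that one draw is fixed at the end of maintenance and before DBPCFC2. Any serum wanted after DBPCFC2 should be listed as a separate exploratory time point and not used as the endpoint value.

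The cost is one schedule cell plus a short alignment of three sections, made by amendment. If any samples have already been collected, record the actual draw date relative to the last dose and to DBPCFC2, so that on-dose and off-dose values can be told apart.

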1 BACKGROUND AND RATIONALE

1.1 Background

Avoidance of allergenic foods and ready access to self-injectable epinephrine during an incident are the standard of care for food allergy. Unfortunately, for a ubiquitous food such as peanut, the possibility of an inadvertent ingestion is great. Symptoms occurring because of these accidental exposures can vary from mild local reactions to life-threatening anaphylaxis.

CONFIDENTIAL

Due to the persistence of allergic reactions and the lack of effective treatment, allergen-specific immunotherapy (IT) is being actively investigated as a treatment option for people with peanut allergy. Effective peanut oral immunotherapy (OIT) would benefit participants by inducing a loss of clinical sensitivity to peanut, particularly if such a change was long-lasting. An understanding of the immune mechanisms of peanut-specific OIT is vital to ensure the eventual, successful treatment of all peanut-allergic participants.

In addition, several groups have recently reported on the use of oral or sublingual IT for other food allergies, including primarily milk, peanut, and egg [? ? ? ? ?]. The preliminary evidence of these studies supports efficacy with respect to clinical desensitization. There remains, however, a great deal to be learned from additional trials. In particular, existing data do not adequately address the question of tolerance and few studies have applied sophisticated laboratory techniques to investigate mechanisms.

1.2 Rationale for Selection of Study Population

This protocol is designed to identify participants who have persistent peanut allergy. By specifically targeting participants who are at the highest risk for life-long peanut sensitivity, we anticipate that we might maximize the benefits of desensitization and/or clinical tolerance induction. By including in our protocol design a post-therapy challenge after a significant allergen avoidance period, we will better distinguish true tolerance from desensitization and some of the immune changes associated with varying clinical outcomes. A blinded placebo control group is included, to control for possible changes in clinical sensitivity over time independent of therapy. The selection of older adolescents and adults will also allow us to better study immunological changes using assays that require blood volumes that would not be feasible to obtain in a younger population.

1.3 Investigational Product(s) / Intervention(s)

The product that will be used in the proposed clinic trial is partially defatted peanut flour. Peanut is currently licensed as a food product in the United States. The peanut flour proposed for use in this study will be purchased in bulk from the Golden Peanut Company, located in Blakely, Georgia. The company states that the product is manufactured under GMP for food products. No other allergens are processed at this facility. This peanut flour is not stored with any other allergens. The amount of peanut ingested orally will change as the study progresses and the doses referred to throughout the protocol will be in terms of mg of protein content.

The placebo will be toasted oat flour. The oat flour proposed for use in this study will be purchased in bulk from the Montana Gluten Free Processors, located in Belgrade, Montana. The company states that the drug is manufactured under GMP for food products. No other allergens such as peanuts, tree nuts, wheat, corn, and soy are processed at this facility. This oat flour is not stored with any other allergens. The amount of oat flour ingested orally will change as the study progresses and will be matched to the equivalent dose of peanut flour by weight.

13 of 68

1.4 Rationale for Selection of Investigational Product(s) / Intervention(s) and Regimen

This product has been used in other trials and has been shown to contain the major peanut allergens. Toasted oat flour was selected for the placebo because it is the most similar to peanut flour in appearance and texture and is free from major allergens.

The inclusion of a post treatment avoidance period of 12 weeks is intended to address whether lasting immunological changes have been induced. This is comparable to published trials and long enough to suggest long-lived immunological tolerance without being so long so as to be impractical for study recruitment and retention.

We will measure the following mechanistic outcomes for each of the three time points (baseline, on maintenance therapy and following avoidance):

- The frequency of each of the CD4 T cell subsets defined by cell surface markers (e.g., CD45RA, CD25, etc).
- The frequency of each of four populations of CD4 T cells: resting T effector, activated T effector, native Treg and induced Treg.
- The frequency of IL-13, IFN- γ and IL-10 expressing populations within the activated and resting Teff subsets.
- The frequency of antigen-expanded Treg as defined by a methodology such as CFSE dilution and FoxP3 intracellular staining or equivalent and of cytokine expressing populations as demonstrated by intracellular cytokine staining or equivalent methodology.
- Global (e.g., Illumina, Affymetrix, etc) or targeted (e.g., nanostring, qPCR, etc) transcriptional gene expression patterns from activated and resting Treg and Teff subsets from participants divided evenly between the following groups: successful tolerance, partial tolerance, failed tolerance, placebo arm;
- Global (e.g., Illumina, Affymetrix, etc) or targeted (e.g., nanostring, qPCR, etc) transcriptional gene expression
 patterns from antigen-expanded or otherwise enriched T cells from 3 non-overlapping pools of subject
 samples from each of the same four clinical groups: successful tolerance, partial tolerance, failed tolerance,
 placebo arm;
- TCR parallel sequencing-based analysis of T cell repertoire of effector and regulatory subsets defined by expression of key phenotypic markers (e.g. CD45RA+CD25+FoxP3+; CD45RA-CD25+++FoxP3+; CD45RA-CD25+/-IL-13+; CD45RA-CD25+/-IL-10+; CD45RA-CD25+/- IFN-?+ by flow cytometry or other methodology).
- T cell repertoire of in vitro expanded or enriched (e.g. by tetramer binding) T cell populations.

These studies will be carried out by ex vivo sorting of 100-300 million PBMC and in vitro expansion or enrichment starting with 60-100 million PBMC. In large part, the cell number requirement is driven by the low frequency of induced T reg and of antigen-specific CD4 T cells.

